#### 4.2.4 Crude incidence and relativ risk estimates

##### 4.2.4.1 Odds ratio and 100\*(1- $\alpha$ )% confidence interval

For an investigational drug group with  $n_1$  subjects at risk, independent from the control group (e.g. placebo or comparator) with  $n_0$  subjects at risk, of whom  $x_1$  and  $x_0$  experience a certain event with probability  $\pi_1$  and  $\pi_0$  respectively, the odds ratio is estimated as

$$\frac{p_1/(1-p_1)}{p_0/(1-p_0)}$$
 with  $p_1 = x_1/n_1$  and  $p_0 = x_0/n_0$ . A conditional exact 100\*(1- $\alpha$ )% confidence interval

will be obtained by using the SAS procedure PROC FREQ with statement EXACT OR.

##### 4.2.4.2 Risk difference and 100\*(1- $\alpha$ )% confidence interval

For an investigational drug group with  $n_1$  subjects at risk, independent from the control group (e.g. placebo or comparator) with  $n_0$  subjects at risk, of whom  $x_1$  and  $x_0$  experience a certain event, the risk difference is estimated as  $p_1 - p_0$  with  $p_1 = x_1/n_1$  and  $p_0 = x_0/n_0$ .

Exact unconditional confidence limits for the risk difference will be obtained with SAS procedure PROC FREQ and option RISKDIFF in the TABLES statement, specifying the RISKDIFF option also in the EXACT statement.

#### 4.2.5 Exposure adjusted incidence rate and related risk estimates

##### 4.2.5.1 Exposure adjusted incidence rate and 100\*(1- $\alpha$ )% confidence interval

It will be assumed that for each of  $n$  subjects in a clinical trial the time  $t_j$  ( $j=1, \dots, n$ ) to the first occurrence of a certain event is observed, or if the event was not experienced, the (censored) time to the end of the observation period. The sequence of first occurrences of an event will be modeled to follow approximately a Poisson process with constant intensity  $\theta$ . The rate

parameter  $\theta$  will be estimated as  $\lambda = D/T$ , where  $T = \sum_{j=1}^n t_j$  and  $D$  is the number of subjects with

at least one event. Conditionally on  $T$ , an exact 100\*(1- $\alpha$ )% confidence interval for a Poisson variable with parameter  $\theta T$  and observed value  $D$  can be obtained based on ([Garwood, 1936](#)),

from which an exact  $100*(1-\alpha)\%$  confidence interval for D/T will be derived as follows ([Sahai, 1993](#); [Ulm, 1990](#)):

$$\text{Lower confidence limit } L = \frac{0.5c_{\alpha/2,2D}}{T} \text{ for } D>0, 0 \text{ otherwise,}$$

[figure not shown]
$$\text{Upper confidence limit } U = \frac{0.5c_{1-\alpha/2,2D+2}}{T}$$

[figure not shown]
where  $c_{\alpha,k}$  is the  $\alpha$ th quantile of the Chi-square distribution with  $k$  degrees of freedom.

The example below shows how this should be handled for cases where subjects switch treatment. In particular for summarizing ‘Any AIN’ as a group, one should take into consideration the sequence of treatments while calculating exposure time for subjects.

**Table 4-3 Examples for calculating exposure time for incidence rates (IR)**

1st treatment	1st exposure	2nd treatment	2nd exposure	Event days (in terms of study day)	Exposure for IR
Placebo	100 days	150 mg	200 days	50 (1st trt) 110 (10 days into 2nd trt)	Placebo: 50 days (event) 150 mg: 10 days (event) Any AIN: 10 days (event)

#### 4.2.7 Details for Total vdH-mTSS analysis

##### 4.2.7.1 Linear Extrapolation (LE)

For the linear extrapolation consider the following variables:

- BLDay : day BL visit occurred
- W16Day/W24Day: day week 16/24 visit occurred
- W16Day/W24Day - BLDay: number of days between week 16/24 visit and baseline visit
- BL16/BL24: baseline score based on imputation algorithm using week 16/24 data.
- Wxx change from BLxx\_imp: week xx change from baseline following application of imputation algorithm using week xx data

Linear Extrapolation from W16 to W24 formula is as follows:

[figure not shown]
$$1. \quad W24 \text{ change from } BL\_imp = \frac{W16 \text{ change from } BL16}{W16 \text{ Day} - BL \text{ Day}} * (W24 \text{ Day} - BL \text{ Day});$$

Note: W24 Day is the assessment day of week 24 visit; if missing, use week 24 target day 169.

2.  $BL24\_imp = BL24 \text{ if available; otherwise } = BL16$ ;
3.  $W24\_imp = BL24\_imp + W24 \text{ change from } BL\_imp$ .
4. If  $W24\_imp < 0$  then set to 0 or if  $W24\_imp > \text{max attainable score}$  replace by maximum score.

For primary analysis (LE Method 1), placebo non-responders (rescued at W16) will be considered as missing at week 24 and LE will be used to extrapolate week 24 data from week 16 as for any other missing week 24 data.

For sensitivity analysis (LE Method 2), all observed week 24 data will be used. Only missing week 24 data will be imputed from LE.

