5.5.4 Instructions for prescribing and taking study treatment

Study treatment (150 mg secukinumab and placebo) will be administered by s.c. PFSs throughout the study. Administration of study treatment will occur at the study site through Week 52. Administration of study treatment must occur after the study assessments for the visit have been completed. After Week 52, subjects will be allowed to self-administer the study treatment at home during the optional visits in which there are no scheduled assessments at the site (see Home Administration in [Table 6-2](#) below).

The PFS with the ready-to-use study treatment solution will be provided by the site staff to the subject. Detailed instructions on the self-administration of the study treatment will be described in the Instructions For Use (IFU) and provided to each subject.

At the BSL visit, subjects will be instructed by the site staff, utilizing the IFU, on how to self-inject using a PFS. Subjects will be asked to raise questions, if they have any, and then to proceed with self-injection. At the Week 1 visit, subjects will be asked to refer to the IFU and to proceed directly with self-injection of the study drug (i.e., no prior retraining) for the remainder of the trial. However, if the subject is not comfortable self-injecting the study treatment, then the site staff may administer it for the subject.

All study treatment kits assigned to the subject during the study will be recorded in the IRT.

The first study treatment administration will occur at the BSL/randomization visit only after eligibility criteria have been confirmed, all study scheduled BSL assessments have been performed and the scheduled blood samples have been drawn.

At each subsequent visit, all study assessments, including the completion of Patient Reported Outcomes (PROs), (as applicable per [Table 6-1](#) and [Table 6-2](#)), should be completed prior to the self-injection of study treatment.

The investigator should promote compliance by instructing the subject to attend the study visits as scheduled and by stating that compliance is necessary for the subject's safety and the validity

of the study. The subject should be instructed to contact the investigator if he/she is unable for any reason to attend a study visit as scheduled or if he/she is unable for any reason to take the study treatment as prescribed.

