6.4.2 Radiographic assessments

Separate radiographs of each hand/wrist (PA) and each foot (AP) will be taken at BSL, Week 16/24, 52, and 104. Bone erosion, joint space narrowing (JSN), and total radiographic scores will be determined using a PsA modified van der Heijde-Sharp (vdH-S) scoring method ([van der Heijde et al 2005](#)) that includes the second through fifth distal interphalangeal (DIP) joints of each hand. Erosions (0–5 in the hands and 0–10 in the feet) and JSN (0–4) will be graded separately in six wrist joints, all metacarpal phalangeal, proximal interphalangeal and DIP joints of each hand, and the first interphalangeal joint and all metatarsal phalangeal joints for each foot. The total radiographic score (hands and feet combined) ranges from 0 to 528, with higher scores indicating more articular damage. The maximum total erosion score is 320. The maximum total JSN score is 208.

The change in the Van der Heijde modified Sharp score is calculated against the BSL value. Radiologists will be trained on the X-ray acquisition and further details will be provided in a manual for the radiologists, e.g. joint placement and beam positioning.

In case of analogue X-rays films, the original film will be sent to the central reading CRO and will undergo quality control and will be digitized. Standard film and cassettes will be provided

[figure not shown]
to all centers that do not produce digital X-rays. In case of digital equipment, sites need to confirm minimum requirements with the imaging CROs. Digital X-rays will be transferred electronically.

In case of insufficient quality, the center will be advised and trained on any quality issues prior to the repeat X-ray and to keep any repeat X-rays to a minimum.

Subjects who are non-responder at Week 16 (not achieving a $\geq 20\%$ improvement from baseline in both TJC and SJC) will have their hands/wrists and feet X-rays taken at this visit (Week 16) and at Week 24 visit. Subjects who are responder at Week 16 ($\geq 20\%$ improvement from baseline in both tender and swollen joint counts) will have their hands/wrists and feet X-rays taken at Week 24.

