**Table 4-2 Rules for flagging variables**

Timing of measurement	Type of data	Rule
Baseline	All data	
The last non-missing measurement made prior to or on the date of administration of the first dose of study treatment (the reference start date / Day 1). If a patient did not receive any dose of study treatment then the randomization date will be used. Only date part is considered if just one assessment on Day 1.
 
If there are multiple assessments on Day 1, following rules will apply:
 

a. If assessment time exists,

• select the last available measurement prior to reference start date/time considering time;

• if no measurement prior to reference start date/time considering time, select the earliest measurement post reference start date/time considering time .

b. If assessment time does not exist, select the available measurement from the lowest CRF visit number.

 
For X-ray, a baseline value is the last measurement prior to dosing if available. Otherwise, take the first value within 30 days post dosing.
 
For MRI, a baseline value is the last measurement prior to dosing if available. Otherwise, take the first value within 7 days post dosing.

Post-baseline efficacy	All data	
For visits without switch of treatment in the window, the measurement closest to the target will be used. In the event two measurements are taken equally apart (e.g. 1 before target date and 1 after) the first one will be used.
 
For visits during which the patient switches from placebo to AIN the following will be done based on whether or not the patient met the rescue criteria:
 

• If the analysis visit window is <= week 16(for non-responders) or week 24 (for responders), then:

Timing of measurement	Type of data	Rule

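### When a scored film is not taken on the visit day, the SAP 4.2.7.1 extrapolation divides a film-to-film change by visit-to-visit days and mis-scales that subject's imputed Week 24 mTSS change; the trial-level effect is small

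*SAP*

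**What the plan says.** SAP 4.2.7.1 gives the linear extrapolation used in the primary mTSS analysis. The Week 16 change from baseline is divided by (W16Day - BLDay) and multiplied by (W24Day - BLDay). The days are defined by visit: "BLDay : day BL visit occurred" and "W16Day/W24Day: day week 16/24 visit occurred", and the interval is the "number of days between week 16/24 visit and baseline visit". A note adds: "W24 Day is the assessment day of week 24 visit; if missing, use week 24 target day 169".

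SAP Table 4-2 sets the baseline film. "For X-ray, a baseline value is the last measurement prior to dosing if available". "Otherwise, take the first value within 30 days post dosing".

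The extrapolation applies to every placebo subject rescued at Week 16 who has the films it needs, even if a Week 24 film was taken, and to any other missing Week 24 score with baseline and Week 16 assessments (SAP 2.6.2.2 and 4.2.7.1). The estimand in SAP 2.6.2.2 assumes that progression continues at the rate seen up to Week 16.

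**The concern.** A rate needs a numerator and a denominator that cover the same time. The numerator here is the difference between two films. The denominator is the time between two visits. They agree only if each film is taken on its visit day. Table 4-2 expressly allows a baseline film that is not, and neither that table nor SAP 4.2.7.1 changes BLDay for such a subject. With a film 30 days after dosing, the change covers 82 days but is divided by 112, which does not give the rate that the estimand names.

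The placebo arm is the most exposed. The rationale for Protocol Amendment 1 expects about 66% of placebo and 33% of secukinumab subjects to be Week 16 non-responders. Rescued placebo subjects are extrapolated regardless, whereas secukinumab non-responders use their observed Week 24 score if they have one. Those who followed the original protocol had no Week 24 film (SAP 2.12.4.1), so some active subjects are extrapolated too. The structural hypotheses H4 to H6 must all be rejected before the second family is tested.

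**Working it through.** **The plan's own figure.** The documents state no extrapolation factor. They do state the power of the mTSS comparison (Protocol 9.7, SAP 3), which gives a scale for any shift. Inputs: SD 1.132 active and 2.435 placebo, difference 0.52, 220 versus 330 subjects, two-sided alpha 0.05/3.
- SE = sqrt(1.132²/220 + 2.435²/330) = 0.1542; Satterthwaite df about 498.
- Power = 83.3% (noncentral t) or 83.6% (normal approximation). The stated 83% is reproduced.

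**Days.** Day 1 is the first dose (SAP Table 4-1), given at the baseline visit (Protocol 5.5.4), so BLDay = 1. SAP 4.1.1 puts Week 4 at Day 29, which is 7 x week + 1, so Week 16 is Day 113. Week 24 is Day 169 (SAP 4.2.7.1).

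**Factor as written, on schedule.** (169 - 1)/(113 - 1) = 168/112 = 1.500.

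**Factor on film dates, baseline film d days after Day 1.** (168 - d)/(112 - d):

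| d (days) | Film-date factor | Rule as written |
|---|---|---|
| 0 | 168/112 = 1.500 | exact |
| 7 | 161/105 = 1.533 | 2.2% too small |
| 14 | 154/98 = 1.571 | 4.5% too small |
| 30 | 138/82 = 1.683 | 10.9% too small |

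For d = 30, the error is 1.500/1.683 - 1 = -10.9%. Only the 30-day limit is documented; 7 and 14 days lie within it.

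**Which target.** The film-date factor carries the change from the actual baseline film to Day 169. Observed Week 24 changes from a late baseline film cover the same shorter span and are not rescaled, so this factor puts imputed and observed values on one footing. If the target were a full 168-day change, the factor at d = 30 would be 168/82 = 2.049 and the shortfall 26.8%, but observed changes would not match it.

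**Trial-level shift.** The share of late films is not given. Assumptions: placebo changes by 0.52 over 168 days (active change zero), 66% of placebo extrapolated, every late baseline film 30 days late.
- Week 16 change on such films: 0.52 x 82/168 = 0.254.
- Error per affected subject: 0.254 x (1.500 - 1.683) = -0.046.
- Shift in placebo mean at 10% late: 0.66 x 0.10 x (-0.046) = -0.003. At 1%, 5% and 20% late it is -0.0003, -0.0015 and -0.0061.
- Power by the normal approximation moves from 83.6% to 83.1% at 10% late and 82.6% at 20%.
- With an assumed placebo change of 1.0 (difference held at 0.52), the shift at 10% late is -0.0059 and power 82.6%.

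**Other offsets, purely as assumptions.** A baseline film 28 days before dosing: 196/140 = 1.400, rule 7% too large. A Week 16 film 14 days after the visit: 168/126 = 1.333, rule 12.5% too large. If 10% of extrapolated placebo subjects had such a Week 16 film, the shift would be 0.66 x 0.10 x 0.125 x 0.52 = +0.004, assuming the rate is unchanged after the visit.

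**The case against.** The strongest reply is that the formula is exact as the trial is scheduled. Films are planned at the visits (Protocol 6.4.2), and the first dose follows only after "all study scheduled BSL assessments have been performed and the scheduled blood samples have been drawn". The post-dose film is a fallback. This stands, and it limits the point to subjects whose films are off the visit day.

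A second reply is that the wording may already mean the film date. The Week 24 note speaks of an assessment day, and SAP 4.1.1 maps assessments to analysis visits by the day they occurred. But the definitions of BLDay and W16Day carry no such wording, so two programmers could choose different dates. That supports clarifying the text.

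A reader might infer three stronger things that the documents do not support.

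- **That late Week 16 films inflate placebo progression.** Protocol 6.4.2 foresees retraining ("trained on any quality issues prior to the repeat X-ray") but gives no timing for repeats. For a placebo subject switching at Week 16, Table 4-2 takes a measurement on or before the switch and uses a later one only if there is none. Unreadable joints can also be imputed (SAP 2.12.4.1), so a poor film may still yield a score. The 14-day case is possible but not documented.
- **That the no-progression cut-off of 0.5 is generally affected.** Assuming whole-number joint scores, two-reader mean changes move in steps of 0.5. A Week 16 change of 0 or less stays at or below 0.5. A change of 0.5 becomes 0.64 at the lowest factor considered (both assumed offsets together, 196/154 = 1.273) and 0.84 at the highest (1.683), so it is above 0.5 throughout. Classification can change only with three-reader means (1/3 x 1.500 = 0.50, but 1/3 x 1.683 = 0.56) or imputed fractional scores.
- **That the gatekeeping structural comparison is at risk.** The shifts above are too small for that. The planned sensitivity analyses (Protocol 9.5.1) also include LOCF, which does not use the factor.

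**Conclusion.** The point holds in a limited form. SAP 4.2.7.1 is defined on visit days, Table 4-2 permits a baseline film up to 30 days after dosing, and no text provided links the two. For such a subject the imputed Week 24 change is too small by up to 10.9%, taking the change between the scored baseline film and Day 169 as the target. When progression is positive, the one documented case shrinks placebo progression and so works against secukinumab.

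Films taken on the visit day give no error. Because the share of off-visit films is not stated, the trial-level effect cannot be fixed; under the assumptions shown it is about -0.003 in the placebo mean at 10% late films and -0.006 at 20%. It would be unsafe to read this as a claim that extrapolated changes are wrongly scaled in general, or that the primary mTSS analysis is undermined. It is an inexpensive correction to a stated rule.

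**What to change.** In SAP 4.2.7.1:

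1. Define BLDay and W16Day as the acquisition dates of the films that were scored.
2. State which day W24Day takes when no Week 24 film exists or when the Week 24 score is set to missing for a rescued placebo subject, for example target Day 169.
3. Report, by arm, how many extrapolated subjects have a baseline or Week 16 film off the visit day, and by how many days.

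The cost is a few words in the definitions and one short summary table. The 30-day rule in Table 4-2 already needs the film date relative to dosing, so no new data should be required.
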